9.1.2. Populations analysed, evaluability and limitations / evaluation of Bias

The statistical analyses will be performed based on the following subject populations. The definition of the populations will be finalized after a data review meeting.

9.1.2.1 The Intent-to-Treat efficacy population (ITT)

This population will consist of the entire population enrolled (i.e. assigned a kit number). The ITT population will be used for all variables except the safety variables.

9.1.2.2 The Safety population (All subject treated [APT])

This population will consist of the Intent-to-Treat population, after exclusion of subjects who never used the treatment with certainty based on monitoring report. The APT population will be only used for the safety variables (AEs).

9.1.2.3 Missing values

The last observation carried forward (LOCF) method will be used to impute missing values of global assessment scores (GAI and IGA). If no post-baseline data are available, baseline will be carried forward. Thus, the number of subjects will not vary at each visit. The other missing values will not be replaced (observed data).

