5.4. CLINICAL TRIAL FLOW CHART

PROCEDURES	CLINICAL TRIAL VISITS				
	Visit 1	Visit 2	Visit 3	Visit 4	Visit 5
	Baseline	Week 2 (±1 d)	Week 8 (±3 d)	Week 12 (±3 d)	Week 16 (±5 d)
Informed consent/Photography Consent ^b	X				
Inclusion/Exclusion Criteria	X				
Demographics/ Relevant medical history/ Prior therapies ^c	X				
Urine Pregnancy test (UPT) ^d	X		X	X	X
Investigator's Global Assessment (IGA)	X	X	X	X	X
Global Assessment of Improvement				X	X ^a
PIH evaluation ^e	X	X	X	X	X
Local tolerance assessment	X	X	X	X	X
Photographs ^b	X ^h	X	X	X	X
Concomitant therapies	X	X	X	X	X
Adverse events ^f	X	X	X	X	X
Dispensation of investigational products	X		X		
Dispensation of non-investigational products	X		X		
Return of investigational products			X		X
Subject Diary/Compliance ^g		X	X	X	X
DLQI-cDLQI questionnaire	X			X	X ^a
Subject satisfaction questionnaire				X	X ^a
Cosmetic acceptability questionnaire					X ^a
Exit form					X ^a

- To be performed at Week 16 or before in case of early termination.
- Photography consent and standardized photography (mandatory criteria for inclusion in the trial).
- Only prior therapies that were stopped within 6 months of the baseline visit and that may have an impact on inclusion/exclusion criteria should be recorded. Treatment that continues after baseline should be recorded on the Concomitant Treatment Form of the CRF.
- UPT will have sensitivity down to at least 25 IU/L for hCG. UPT is mandatory at baseline, week 8, week 12 and week 16/early termination in female subjects
- If PIH present at baseline visit.
- Adverse event onsets after subject signature of the informed consent form should be recorded on the AE Form of the CRF.
- Subject diary is a diary which will be given to the subject to report the treatment application
- Sponsor Medical Expert will review the clinical evaluation of acne and give his confirmation for inclusion of subjects into the trial.

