- a. Dispense to the subject the baseline investigational product from the adequate subject kit according to the Prescription Form,
 - b. Affix the tear-off portion of the label on the Product Dispensation Log,
 - c. Dispense to the subject the associated non-investigational products with explanations how and when to use them,
 - d. Dispense the subject participation card to the subject,
 - e. Provide appropriate verbal and written instructions on how to properly use the investigational product. The **first application** of investigational product will be conducted by the subject under the direction of the Product Dispenser **before** leaving the investigational site,
 - f. Remind the subject to not to apply the investigational product the first evening,
 - g. Dispense a subject Diary and provide verbal instruction on how to complete the Diary after each product application,
 - h. Emphasize the importance of complying with the given instructions and treatments, instruct the subject to bring back the subject's diary at the next visit,
 - i. For all female subjects, emphasize the guidelines about contraception and risks in case of pregnancy,
19. Ask the subject to complete baseline DLQI/cDLQI questionnaire,
20. Schedule the next follow up visit in two weeks \pm 1 day.

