5.5.6. Early termination visit

In case of early termination, the procedures corresponding to the next theoretical visit should be performed (e.g. if a subject discontinues after week 2, complete the week 8 visit procedures). Additional final procedures will be conducted as indicated in the trial flow chart section 5.4.

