7.2.2. Global Assessment of Improvement (GAI)

At Week 12 and Week 16/Early termination, the evaluator will evaluate the degree of acne improvement **versus baseline** using the Global Assessment of Improvement score as follows:

Category	Score	Description
Excellent improvement	0	All or nearly all signs and symptoms cleared (around and more than 90% improvement from Baseline). Whether no, or only minimal residual signs and symptoms remain
Very good Improvement	1	Majority of the signs and symptoms have resolved (about 75% improvement from Baseline)
Good Improvement	2	Significant improvement, but many signs and symptoms remain (about 50% improvement from Baseline)
Minimal Improvement	3	Slight overall improvement, but not clinically significant (about 25% improvement from Baseline)
No Change	4	Overall severity similar to Baseline
Worse	5	Worse than Baseline

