9.1.1. Variables to be statistically analyzed

The following variables will be analyzed:

Subject reported outcome variable

- *DLQI/cDLQI at Baseline, Week 12 and last visit*
- *Subject satisfaction questionnaire at Week 12 and last visit*

Efficacy variables

- *IGA score: % of subjects across scores at each visit*
- *GAI score: % of subjects across scores at Week 12 and last visit*

Safety variables on safety population

- *PIH: Raw value at each visit and % change from baseline at each post-baseline visit*
- *Local tolerance: Raw value at each visit and worst-score across visit, % of Subjects across scores at each post-baseline visit*
- *Incidence of adverse events*
- *Incidence of serious adverse events*

Other variables

- *Cosmetic acceptability questionnaire at last visit*

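### Does the missing-value rule break down for GAI, which has no baseline score to carry forward?

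*Combined protocol and SAP*

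**What the plan says.** Section 9.1.2.3 names the two global scores, GAI and IGA, for last observation carried forward. It then gives the fallback and its consequence: "If no post-baseline data are available, baseline will be carried forward. Thus, the number of subjects will not vary at each visit". Only values other than these two scores are left as observed.

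The two scores are collected differently. Under Section 7.2.1 and the flow chart in Section 5.4, IGA is scored at all five visits, baseline included. GAI is not: "At Week 12 and Week 16/Early termination, the evaluator will evaluate the degree of acne improvement" (Section 7.2.2). Its score 4, No Change, is defined as "Overall severity similar to Baseline".

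Section 9.1.1 plans the table as "GAI score: % of subjects across scores at Week 12 and last visit", and Section 9.1.2.1 places it on the ITT population, meaning everyone given a kit number. For subjects who leave early, the flow chart note on GAI reads "To be performed at Week 16 or before in case of early termination", and Section 5.5.6 adds "Additional final procedures will be conducted as indicated in the trial flow chart section 5.4". Section 4.5.6 qualifies this: the exit evaluation is made where it is possible.

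**The concern.** One sentence governs two scores, and read literally it fits only one of them. Two groups of subjects look stranded.

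- **No GAI at any time.** A subject lost before Week 12 who attends no exit visit has nothing to carry forward and no baseline GAI to fall back on. If that subject has a Week 2 or Week 8 IGA, it is also unclear whether the fallback condition, no data after baseline, is met.
- **Week 12 missed, Week 16 attended.** No earlier GAI exists, and the fallback seems not to apply because a later GAI does. The promise of a constant number of subjects would then fail for the Week 12 GAI table.

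GAI is one of two efficacy variables. If the rule could not be run, two programmers might produce different denominators and different percentages, and the convention might be chosen with open-label data in view.

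**Working it through.** The plan gives no figure to reproduce: Section 9.2 offers no statistical basis for 60 subjects, and no dropout or response rate is stated. The only quantitative claim to test is the constant number of subjects.

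**Step 1. Apply the rule to each missing-data pattern** (1 = value available, 0 = missing). For IGA, baseline counts as an observation that can be carried.

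| Pattern | IGA, every visit | GAI Wk 12 / Wk 16, literal | Score 4 only if no GAI ever | Score 4 whenever no earlier GAI |
|---|---|---|---|---|
| Completer | 1 | 1 / 1 | 1 / 1 | 1 / 1 |
| Early exit, GAI done at exit | 1 | 1 / 1 | 1 / 1 | 1 / 1 |
| Lost after Wk 2 or Wk 8, no exit visit | 1 | 0 / 0 | 1 / 1 | 1 / 1 |
| No data after baseline | 1 | 0 / 0 | 1 / 1 | 1 / 1 |
| Wk 12 missed, Wk 16 attended | 1 | 0 / 1 | 0 / 1 | 1 / 1 |
| Wk 12 done, lost before Wk 16 | 1 | 1 / 1 | 1 / 1 | 1 / 1 |

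The literal reading fails in three patterns. The last column delivers the constant number that Section 9.1.2.3 promises.

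**Step 2. Is the last column a fair reading?** Take a subject who misses the Week 2 IGA and attends Week 8. This subject also has later data and no earlier post-baseline value. The number for IGA stays constant only if baseline counts as an observation, or if the fallback is judged as of the visit being filled. Either reading, applied equally to GAI, gives score 4 at a missed Week 12. So the constant-number sentence is false for GAI only if GAI is read more strictly than IGA.

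**Step 3. Size at the last visit** (assumed N = 60). Let p be the observed share with scores 0 to 2 and m the number with no GAI. Assigning score 4 instead of dropping them gives p × (60 − m)/60.

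| p | m = 1 | m = 2 | m = 3 |
|---|---|---|---|
| 40% | 39.3% | 38.7% | 38.0% |
| 60% | 59.0% | 58.0% | 57.0% |
| 80% | 78.7% | 77.3% | 76.0% |

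If score 4 was intended all along, the change is zero.

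**Step 4. Size at Week 12.** Suppose 36/60 = 60% had everyone been scored, and k subjects were scored only later.

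- Leaving them missing: k = 1 gives 35/59 to 36/59 (59.3% to 61.0%); k = 2 gives 34/58 to 36/58 (58.6% to 62.1%); k = 3 gives 33/57 to 36/57 (57.9% to 63.2%).
- Assigning score 4: the share lies between (36 − k)/60 and 36/60, so the lower ends are 58.3%, 56.7% and 55.0%.

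**Step 5. Heavier loss at Week 12.** Assumed counts are: lost with no GAI / no data after baseline / Week 12 only missed. About 60% of those observed are taken as responders.

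| Counts | Literal n | Share on literal n | Share on all 60 |
|---|---|---|---|
| 1 / 1 / 1 | 57 | 34/57 = 59.6% | 34/60 = 56.7% |
| 3 / 2 / 2 | 53 | 32/53 = 60.4% | 32/60 = 53.3% |
| 6 / 3 / 4 | 47 | 28/47 = 59.6% | 28/60 = 46.7% |

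The gap can reach about 13 points when 13 of 60 are affected. But the literal n drops subjects whom Section 9.1.2.3 says will be imputed, so that column is not a reading the plan offers.

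**The case for a change.** The strongest case for an edit is that no sentence says score 4. A rule that needs interpretation can be interpreted differently, and settling it before the data review meeting costs a line or two. Giving No Change at Week 12 to someone with a real Week 16 rating is also not something the text spells out. And a subject whose IGA had improved by Week 8 before being lost would count as improved in the IGA table and unchanged in the GAI table.

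The first point stands as a fact about the wording. It does not show that two defensible tables would result, because observed-case GAI contradicts both the list of imputed scores and the constant number. The second is a consequence of the plan's choice to impute. Leaving that subject missing, while a subject lost for good receives score 4, would treat the same missing Week 12 value in two ways and abandon the constant number. The third is a real cost of the method, but it follows from using score 4 at all; spelling the convention out would not remove it.

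The plan also limits the exposure. GAI is scheduled at early exit, so subjects with none are mainly those lost before Week 12 who do not return. Section 9.1.3 already prints the number of values for ordinal scores. Section 9.1 assigns data conventions to a separate SAP to be finalised before database lock; that document is not in the file, so whether it states score 4 cannot be checked.

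**Conclusion.** The observation is correct: GAI has no baseline value, and the substitute is implied rather than stated. It is a gap that analysts fill sensibly. Score 4 is the only GAI category that means unchanged from baseline, and it is what carrying baseline forward amounts to on this scale. Read visit by visit, as IGA must be read too, it keeps the full ITT count at Week 12 and at the last visit. Writing the convention down would record that reading and alter no planned table.

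The effect is zero if score 4 was intended. Against an observed-case table it is 1.0 point per subject without a GAI at the last visit for an assumed 60% response, 0.7 at 40% and 1.3 at 80%. These sizes rest on assumed missing counts and response rates. IGA and the subject-reported outcomes are unaffected, and Section 9.1.4 plans no inference that a shift in GAI could disturb.

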2.3.2. Risk-benefit statement related to the clinical trial

Adapalene 0.3% - BPO 2.5% gel is an established and widely used marketed product and considered standard of care by many physicians and expert bodies for the treatment of acne vulgaris. It is therefore considered that exposure to the treatment over 4 months is covered by long-term safety data for the products Adapalene 0.3% and the combination of Adapalene 0.1% - BPO 2.5% which have shown that the safety profile remains stable with a long-term use.

Treatment-related adverse reactions typically associated with use of Epiduo[®] Forte / TactuPump[™] Forte gel include mild to moderate application site reactions, such as skin irritation characterized by scaling, dryness, erythema, atopic dermatitis, eczema, and burning/stinging. These reactions usually occur early in the treatment, and tend to gradually lessen over time.

Any subject is free to discontinue his/her participation in this clinical trial at any time and for whatever reason, specified or unspecified, and without any prejudice. No constraints are to be imposed on the subject, and when appropriate, a subject may be treated with other conventional therapy when clinically indicated.

No invasive method will be conducted during this trial.

Subjects will be followed (especially for Adverse events) regularly during all the trial, approximately once a month for 4 months.

Consequently, based on available safety data and the proposed trial design, no safety issues other than those reported by the labelling are expected following topical administration of Adapalene 0.3% - BPO 2.5% gel.

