9.1.3. Data presentation and graphics

All continuous data will be summarized using usual statistics: number of values, mean, median, standard deviation, minimum and maximum, and by frequency distribution (n, %) for qualitative data. For ordinal data, both frequency distribution and usual statistics will be presented. All tables will be presented by clinical trial treatment and by visit (when applicable).

Therapies that have been stopped before the baseline visit will be presented as prior therapies. Those reported at screening or starting between screening and baseline visits and still continuing after baseline will be classified as concomitant therapies.

The adverse events will be descriptively summarized (n, %) for the safety population (APT). The adverse events will be descriptively summarized (n, %) by relationship to clinical trial treatments within System Organ Class (SOC) and preferred term (MedDRA). Subjects will be descriptively summarized (n, %) by intensity (*i.e.* mild, moderate and severe) of adverse events, SOC and preferred terms. Deaths and serious adverse events will be reported as well as withdrawals due to adverse events. A subject will be counted only once per System Organ Class (SOC) and only

once per preferred term even if more than one occurrence of an event was reported within a SOC or preferred term. In the summary by categories of intensity, the adverse event with the highest intensity will be used. The subject will be counted only once per SOC (highest intensity whatever the AE within the SOC) and once per preferred term (highest intensity whatever the AE within the preferred term).

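### By-visit tolerance and PIH tables count only subjects still in the trial, so if dropout is related to irritation, later visits can show less irritation with no individual improving

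*Combined protocol and SAP*

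**What the plan says.** Section 9.1.2.3 treats two groups of variables differently. For efficacy, "The last observation carried forward (LOCF) method will be used to impute missing values of global assessment scores (GAI and IGA"), with baseline used when nothing later exists, so that the count stays constant across visits. For all remaining variables, "The other missing values will not be replaced (observed data").

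Section 9.1.1 lists the safety summaries:

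- Local tolerance: "Raw value at each visit and worst-score across visit, % of Subjects across scores at each post-baseline visit".
- PIH: "Raw value at each visit and % change from baseline at each post-baseline visit". No worst score is listed.

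Section 5.5.6 says that at early termination "the procedures corresponding to the next theoretical visit should be performed". Section 4.5.6 adds that this is done where possible and that subjects who leave are not replaced. The synopsis and the flow chart (section 5.4) restrict PIH evaluation to subjects with PIH at baseline.

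Section 9.1.3 shows the number of values in each summary and reports withdrawals due to adverse events. Section 2.3.2 says of the known application-site reactions: "These reactions usually occur early in the treatment, and tend to gradually lessen over time".

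**The concern.** A subject who leaves normally has one exit assessment and no score after it. From then on that subject is in neither the numerator nor the denominator of the tolerance and PIH tables. The plan keeps the count constant for IGA and GAI but not for the scores where the outcome may itself be the reason for leaving.

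The trial is descriptive, so its tables are its result. Good tolerability is half of the hypothesis in section 3.2, and section 2.3.2 already leads a reader to expect reactions that fade. Loss of irritated subjects would give the same falling profile as true improvement within subjects. The summaries described in section 9 give a reader no means of telling the two apart.

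**Working it through.** **Inputs.** From the documents: N = 60 planned subjects (section 9.2), no replacement (section 4.5.6), observed data for tolerance and PIH (section 9.1.2.3). The documents give no irritation rate and no dropout rate, so those below are assumptions shown over a range. There is no stated figure to reproduce, because section 9.2 gives no calculation behind the 60.

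**Model.** k subjects score 2 or more at Week 2. Nobody's score ever changes. Then d irritated and e non-irritated subjects leave.

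- Observed share at a later visit = (k − d)/(N − d − e).
- Share by worst post-baseline score = k/N, whoever leaves, as long as each subject has at least one post-baseline score.
- The observed share falls below k/N exactly when d/(d + e) > k/N, that is, when irritated subjects are over-represented among leavers.

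**Local tolerance, k = 15 (15/60 = 25.0%).**

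| Leavers | Later observed share | Worst-score share |
|---|---|---|
| 3 irritated | 12/57 = 21.1% | 15/60 = 25.0% |
| 6 irritated | 9/54 = 16.7% | 25.0% |
| 9 irritated | 6/51 = 11.8% | 25.0% |
| 6 non-irritated | 15/54 = 27.8% | 25.0% |
| 1 irritated, 3 non-irritated (proportional) | 14/56 = 25.0% | 25.0% |

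**Other starting shares.**

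- k = 6: 10.0% falls to 3/57 = 5.3% with 3 irritated leavers.
- k = 12: 20.0% falls to 9/57 = 15.8% with 3, or 6/54 = 11.1% with 6.
- k = 18: 30.0% falls to 15/57 = 26.3% with 3, or 12/54 = 22.2% with 6.

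**PIH.** Assume 40 subjects with PIH at baseline, 10 of them at score 3 (25.0%). If 3 of the 10 leave, the share is 7/37 = 18.9%; if 5 leave, 5/35 = 14.3%. No worst-score line would show the undiluted 25.0%. This needs leavers to have higher PIH scores; leaving because of irritation is not enough by itself.

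**What the proposed display would show.** Take k = 15 with 6 irritated leavers. On a denominator of 60, the later visit shows 9 scoring 2 or more (15.0%), 45 scoring less (75.0%) and 6 who left because of a local reaction or AE (10.0%). In the 54 subjects scored at both visits, the share is 9/54 = 16.7% at Week 2 and 16.7% later. The paired table correctly shows no change, and the leaver row shows where the missing irritation went.

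**The case against.** A reader might infer that irritated leavers disappear from the safety results and that the plan is biased in favour of the gel. The documents do not support that, for these reasons:

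- Local tolerance is not summarised by visit alone. The worst-score summary keeps every subject with one post-baseline score, and the hypothesis in section 3.2 says well tolerated, not fading.
- An exit assessment is expected where possible. Permanent discontinuation for a local reaction is recorded as an AE (section 7.3.2), any increase in PIH score is an AE (section 7.3.1), and AE withdrawals and the number of values are reported (section 9.1.3).
- The direction is not known in advance. Section 4.5.6 lists lack of efficacy, subject withdrawal, loss to follow-up and other reasons for leaving. Section 6.3.6 allows irritation to be managed without leaving the trial.
- Section 2.3.2 is background on the product. No section plans a conclusion about the time course.
- Section 9.1 defers detailed conventions to a separate SAP, which may specify table rows that section 9 does not.

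All of this stands and limits the point. What it leaves open is the time course. The worst score says how bad irritation became, not when or whether it resolved. The AE withdrawal count is not tied to visits or to tolerance scores. A falling number of values shows that subjects are missing, not why. For PIH even the worst score is absent.

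The visit under which an exit score is analysed is also unstated. Section 5.5.6 says which procedures to perform, so filing the score under the next scheduled visit is an inference. It affects only the visit from which a leaver is missing, not the arithmetic.

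**Conclusion.** The point holds in a conditional form. The by-visit tolerance and PIH distributions describe subjects who stay. If irritated subjects are over-represented among leavers, those distributions can show irritation fading with no individual improving. For 15 irritated subjects of 60, the apparent fall is 3.9 points (25.0 − 21.1), 8.3 points (25.0 − 16.7) or 13.2 points (25.0 − 11.8) for 3, 6 or 9 irritated leavers.

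These sizes rest on assumed irritation and dropout rates, static scores and no other leavers. Proportional dropout gives no distortion, and loss of 6 non-irritated subjects gives a rise of 2.8 points. The claim that the bias must favour the gel is therefore not supported; what is supported is that the summaries in section 9 would not let a reader tell which case occurred. The gap is wider for PIH, which lacks a worst-score summary, although any increase in PIH score is still reported as an AE.

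**What to change.** Before the SAP is final:

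1. In the by-visit tolerance tables, use all subjects in the safety population (APT) as the denominator. In the by-visit PIH tables, use APT subjects with PIH at baseline, because a full APT denominator would count subjects whom the flow chart excludes from PIH evaluation. In both, add rows for *left earlier because of a local reaction or AE*, *left earlier for another reason* and *not assessed*.
2. Add a worst post-baseline score summary for PIH.
3. Base any statement that irritation lessens over time on a paired table, Week 2 against each later visit, in subjects scored at both. That table describes stayers, so read it beside the leaver rows and the worst-score table.

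No imputation of safety scores is needed. Carrying scores forward would not be neutral, since it freezes the exit score.

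The cost is SAP wording and table shells. The Exit Form and the AE Form already collect the reasons for leaving, so no new data are required. The downside is slightly longer tables and possibly a less favourable late profile.
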